13.4.2. Reporting Adverse Events to the Responsible IEC/IRB and Health Authorities

Adverse events that meet the IEC/IRB requirements for reporting must be reported within the IEC/IRB's written guidelines. Each clinical site will refer to and follow any guidelines set forth by their Approving IEC/IRB. Each clinical site will refer to and follow any guidelines set forth by their local governing Health Authorities.

The Sponsor will report applicable Adverse Events to the local health authorities according the written guidelines, including reporting timelines.

13.4.3. Event of Special Interest

None

13.5. Reporting of Pregnancy

Subjects reporting pregnancy (by self-report) during the study will be discontinued after the event is recorded as an Adverse Event. Once discontinued, pregnant participants and their fetuses will not be monitored for study related purposes. At the Investigator's discretion, the study participant may be followed by the Investigator through delivery. However, this data will not be collected as part of the clinical study database. Pregnant participants are not discontinued from contact lens or solution related studies for safety concerns, but due to general concerns relating to pregnancy and contact lens use. Specifically, pregnant women are discontinued due to fluctuations in refractive error and/or visual acuity that occur secondary to systemic hormonal changes, and not due to unforeseen health risks to the mother or fetus.

14. STATISTICAL METHODS

14.1. General Considerations

Statistical Analysis will be undertaken by the sponsor or under the authority of the sponsor. A general description of the statistical methods to be implemented in this clinical trial is outlined below.

All data summaries and statistical analyses will be performed using the Statistical Analysis System (SAS) software Version 9.4 (SAS Institute, Cary, NC). Throughout the analysis of data, the results for each subject/eye will be used when available for summarization and statistical analysis. Unscheduled visits will not be summarized separately and will be excluded from the statistical analysis.

Summary tables (descriptive statistics and/or frequency tables) will be provided for all baseline variables, efficacy variables and safety variables by previous wearing experience (i.e. neophyte or previous wearers). Continuous variables will be summarized with descriptive statistics (n, mean, standard deviation [SD], median, minimum and maximum). Frequency count and percentage of subjects or eyes within each category will be provided for categorical data.

14.2. Sample Size Justification

Up to 16 subjects will be enrolled and a minimum of 12 subjects are targeted to complete the study. This is a pilot, descriptive summary study and no statistical sample size estimation was conducted.

14.3. Analysis Populations

Safety Population:

All subjects who were administered any test article excluding subjects who drop out prior to administering any test article. At least one observation should be recorded.

Per-Protocol Population:

All subjects who have successfully completed all visits and did not substantially deviate from the protocol as determined by the trial cohort review committee prior to database hard lock (Per-Protocol Population). Justification of excluding subjects with protocol deviations in the Per-Protocol Population set will be documented in a memo to file.

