1.10	Lens Insertion and Removal Instructions	
The subject will be given instructions on contact lens insertion and removal. A video may be used (https://www.acuvue.ca/contact-lens-care/how-to-put-in-and-take-out-contacts) in addition to verbal instructions.

1.11	Lens Insertion	
The subject will attempt to insert a contact lens in each eye. After the initial instructions are given to the subject, the lens will be assigned and the starting time should be recorded prior to attempting to apply a lens to each eye.
 
If a subject has not successfully inserted a lens in the first eye after 20 minutes, they can stop the process on the first eye and attempt to insert a lens on their fellow eye.
 
If a subject has not successfully inserted a lens in the fellow eye after 20 minutes, they can stop the process and proceed to the Exit Visit.
 
The subject will be allowed to voluntarily end the contact lens insertion activity at any time prior to the 20-minute time point.
 
Record the time of insertion for each eye or the time of stopping the insertion process for each eye.
 
After the subject has successfully inserted a lens in

Visit 1: Treatment 1		
Step	Procedure	Details
		
the first eye, they can attempt to insert a lens on their fellow eye following the same guidelines and instructions as the first eye.
 
Note: A Patient Instruction Guide will be given to the subject in any study where a lens is placed on eye. The subject may wear the study lenses only at the clinical site.

1.12	Subject Reported Ocular Symptoms	Subjects will respond to a verbal open-ended symptoms questionnaire.

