1.13	Lens Removal	
The subject will attempt to remove a contact lens from each eye. After the initial instructions are given to the subject, the starting time should be recorded prior to attempting to remove the contact lens from each eye. A video may be used (https://www.acuvue.ca/contact-lens-care/how-to-put-in-and-take-out-contacts) in addition to verbal instructions.
 
After the subject has successfully removed a lens from the first eye, they can attempt to remove the lens from their fellow eye following the same guidelines and instructions as the first eye.
 
If a subject has not successfully removed the contact lens from the first eye after 20 minutes, the doctor or technician can remove both lenses for the subject and then have them proceed to the Exit Visit.
 
Record the time of removal for each lens or the time of stopping the removal process for each lens
 
All worn lenses will be discarded

FINAL EVALUATION

The final evaluation will ordinarily take place immediately following the last scheduled follow-up visit per the study protocol. It may also take place at any point the subject discontinues the study or is terminated from the study.

Final Evaluation		
Step	Procedure	Details
	Final Exam Form	Indicate if the subject completed the study successfully. If subject discontinued from the study, indicate the reason.

Final Evaluation		
Step	Procedure	Details
	Subjective spherocylindrical Refraction and Visual Acuity	Perform bare-eye subjective spherocylindrical refraction with a phoropter and record the best corrected distance visual acuity to the nearest letter (OD, OS, and OU). [REDACTED]
	Exit Slit Lamp Biomicroscopy	FDA Slit Lamp Classification Scale will be used to grade the findings. If the clearance of the fluorescein needs to be expedited, preservative-free rewetting drops or saline may be instilled. [REDACTED]
	Signature	Record any additional information on the page provided and sign the form. [REDACTED]

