14.4. Level of Statistical Significance

All planned analysis for this study will be conducted with an overall type I error rate of 5%.

Primary Analysis Primary analysis:

Primary end points: Overall success rate (as a percentage) of insertion and removal of a contact lens in both eyes

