14.5. Primary Analysis

Not Applicable.

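### Can subjects who fail the insertion or removal task fall out of the denominator of the both-eyes success rate?

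*Combined protocol and SAP*

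**What the plan says.** Sections 2.2 and 14.4 give the endpoint: "Overall success rate (as a percentage) of insertion and removal of a contact lens in both eyes". Section 14.5, where its analysis would be described, reads "Not Applicable".

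Section 14.3 defines two sets and ties neither to the endpoint:

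- **Safety:** "All subjects who were administered any test article excluding subjects who drop out prior to administering any test article", with at least one observation recorded.
- **Per-Protocol:** "All subjects who have successfully completed all visits and did not substantially deviate from the protocol". A cohort review committee settles membership before hard lock, and a memo must justify exclusions for deviations.

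Section 14.1 supplies the descriptive method: counts and percentages of subjects or eyes, tabulating "efficacy variables and safety variables by previous wearing experience". Section 14.9 rules out imputation and reports the number of missing values.

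Two items in Section 7.2 also bear on the point. Step 1.11 provides that "The subject will be allowed to voluntarily end the contact lens insertion activity at any time prior to the 20-minute time point". The Final Exam Form says "Indicate if the subject completed the study successfully" and asks for a reason if the subject discontinued.

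**The concern.** A success rate needs a denominator, and here none is named. Each set has wording that could be turned against the failures.

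- A subject who never gets a lens in might be said not to have been administered one. If that subject stopped voluntarily, the stop might be called a drop-out.
- A subject who fails a task might be said not to have completed the visit successfully. The Final Exam Form uses the same adverb and does not define it.

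Section 4.2 says the results will help shape later studies and product strategy, so people who cannot insert a lens are a main finding of the pilot. A set that lost them would overstate feasibility. It could also narrow the contrast between neophytes and previous wearers if the never-lensed were mostly neophytes. The study is open-label and Per-Protocol membership is decided after outcomes have occurred, so the choice could be made with the failures known.

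A smaller worry is that some subjects may exit with removal untried in an eye that has a lens, and no code for that is given.

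**Working it through.** The plan states no success rate, power or sample-size calculation (Section 14.2), so there is no figure to reproduce. The question is mainly one of reading.

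**1. Does *administered* exclude a failed inserter?** Section 6.3, which is headed as the section on administration, says lenses are given to subjects who meet the eligibility requirements and describes what those subjects do as attempting insertion and removal. In Step 1.11, "the lens will be assigned and the starting time should be recorded prior to attempting to apply a lens to each eye". Anyone who starts has therefore been given an article. Step 1.11 also asks for the time at which an unsuccessful attempt stopped, which meets the requirement for one observation. A voluntary stop is a permitted route with its own data item. The natural drop-out before administration is someone who leaves before receiving a lens.

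**2. Does *successfully completed* mean task success?** In Section 14.3 its object is the visits. Section 8.1 defines completion as consent, eligibility and attendance at the scheduled visits, with no task requirement. Step 1.11 sends failed inserters to exit as planned flow. None of the withdrawal reasons in Section 8.2 is failure to handle the lens. The task-success reading would also make the rate S/S = 100% whatever the number of failures S leaves out, which defeats the objective in Section 2.1.

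**3. Does an untried removal leave the composite undetermined?** The planned routes are:

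| Route | Removal untried | Both-eyes result already known |
|---|---|---|
| No lens in either eye | both | failure at insertion |
| One eye inserted, fellow eye not, exit | possibly the lensed eye | failure at insertion |
| Both inserted, first removal fails, staff remove both | fellow eye | failure at removal |

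On each planned route, a failed or stopped task comes before the untried one. The composite is already a failure and needs no imputation. Figure 1 has the technician record success or failure of insertion and removal for each eye, which supplies the data.

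**4. What would the hostile reading cost?** Let N be the starters, S the successes and *a* the never-lensed subjects dropped. The rate moves from S/N to S/(N − a), a ratio of 1/(1 − a/N). All counts below are assumptions.

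| Dropped | N = 16, S = 10 | N = 12, S = 8 |
|---|---|---|
| 0 | 10/16 = 62.5% (exact 95% CI 35.4 to 84.8) | 8/12 = 66.7% (34.9 to 90.1) |
| 1 | 10/15 = 66.7% | 8/11 = 72.7% |
| 2 | 10/14 = 71.4% | 8/10 = 80.0% |
| 3 | 10/13 = 76.9% | 8/9 = 88.9% |
| 4 | 10/12 = 83.3% | not shown |

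For N = 16 the ratio runs from 1.067 (a = 1) to 1.333 (a = 4). With a = 0 nothing changes. Even this reading of the Safety set loses only subjects with no lens in either eye. One-eye failures and removal failures remain. On the reading in steps 1 and 2, the first row applies.

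**The case for a change.** The strongest reply is that a descriptive study's product is its percentage, so being a pilot does not excuse leaving the denominator unnamed. Section 14.3 cites neither 6.3 nor 8.1, adds an adverb that 8.1 lacks, and in its Safety wording can be parsed with the subject as the one who administers. The Final Exam Form could be filled in either way for a task failure. Section 14.1 uses results when available, so a subject with no removal result might be left out. Sections 5.2 and 8.2 also disagree on replacing discontinued subjects, so a failure coded as a discontinuation might be both dropped and replaced.

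It stands that no sentence assigns a set or a scoring rule, and that the size of any inflation would matter if failures were dropped. The step from there to failures being lost does not stand. It requires ignoring the section on administration, the definition of completion and the planned exit route together. The replacement conflict affects this rate only if a task failure is first coded as a discontinuation, which nothing in Section 8.2 directs. Committee discretion is limited too: exclusions are for substantial deviations and need a memo, and failing the task is nowhere called a deviation. With at most 16 subjects at one visit and missing counts tabulated, lost failures would probably be visible.

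The eye-level removal percentage could be selective if computed over attempted eyes only and the two eyes are correlated. It is not the endpoint, there is no bias at zero correlation, and the documents give no basis for a size.

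**Conclusion.** The concern does not call for a change. Section 14.5 leaves the denominator and scoring rule unwritten, but Sections 6.3 and 8.1, Step 1.11 and Figure 1 together lead to one sensible rule: every eligible subject who starts the task counts, and a failed or stopped task is a failure of the composite. On that rule the rate in the worked example stays at 62.5%. The larger figures need both assumed counts and a reading the protocol does not support.

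This rests on two assumptions. The analyst reads Section 14.3 together with the rest of the protocol, and site staff record a task failure as an outcome and not as a discontinuation. One case remains open: a subject who inserts both lenses and is then withdrawn for an unrelated reason before removal. That value would be missing, and Section 14.9 has it counted and shown. The untried-removal point leaves the both-eyes endpoint unaffected.

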14.4. Level of Statistical Significance

All planned analysis for this study will be conducted with an overall type I error rate of 5%.

Primary Analysis Primary analysis:

Primary end points: Overall success rate (as a percentage) of insertion and removal of a contact lens in both eyes

14.5. Primary Analysis

Not Applicable.

14.6. Secondary Analysis

Not Applicable.

14.7. Other Exploratory Analyses

Not Applicable.

14.8. Interim Analysis

Not Applicable.

14.9. Procedure for Handling Missing Data and Drop-Outs

Missing or spurious values will not be imputed. The count of missing values will be included in the summary tables and listings.

14.10. Procedure for Reporting Deviations from Statistical Plan

The analysis will be conducted according to that specified in above sections. There are no known reasons for which it is planned to deviate from these analysis methods. If for any reason a change is made, the change will be documented in the study report along with a justification for the change.

15. DATA HANDLING AND RECORD KEEPING/ARCHIVING

15.1. Electronic Case Report Form/Data Collection

The data for this study will be captured on electronic case report forms (eCRFs) using an EDC system, Bioclinica. An authorized data originator will enter study data into the eCRFs using the EDC system. Data collected on equipment that is not captured in EDC will be formatted to the specification of the JJVC database manager and sent to JJVC for analysis.

The clinical data will be recorded on dedicated eCRFs specifically designed to match the study procedures for each visit. Once completed, the eCRFs will be reviewed for accuracy and completeness and signed by the Investigator. The sponsor or sponsor's representatives will be authorized to gain access to the subject recordation for the purposes of monitoring and auditing the study.

Edit checks, electronic queries, and audit trails are built into the system to ensure accurate and complete data collection. Data will be transmitted from the clinical site to a secure

central database as forms are completed or updated, ensuring information accuracy, security, and confidentiality. After the final database lock, the Investigator will be provided with Individual Patient Profiles (IPP) including the full audit trail on electronic media in PDF format for all of the study data. The IPP must be retained in the study files as a certified copy of the source data for the study.

The content and structure of the eCRFs are compliant with ISO14155:2011.¹

15.2. Subject Record

At a minimum, subject record should be available for the following:

- subject identification
- eligibility
- study identification
- study discussion
- provision of and date of informed consent
- visit dates
- results of safety and efficacy parameters as required by the protocol
- a record of all adverse events
- follow-up of adverse events
- medical history and concomitant medication
- test article receipt/dispensing/return records
- date of study completion
- reason for early discontinuation of test article or withdrawal from the study, if applicable

The subject record is the eCRF or an external record. The author of an entry in the subject record must be identifiable. The first point of entry will be considered the source record.

Adverse event notes must be reviewed and initialed by the Investigator.

16. DATA MANAGEMENT

16.1. Access to Source Data/Document

The Investigator/Institution will permit trial-related monitoring, audits, IEC/IRB review and regulatory inspection(s) by providing direct access to source data/documents. Should the clinical site be contacted for an audit by an IEC/IRB or regulatory authority, JJVC must be contacted and notified in writing within 24 hours.

16.2. Confidentiality of Information

Information concerning the investigational product and patent application processes, scientific data or other pertinent information is confidential and remains the property of JJVC. The Investigator may use this information for the purposes of the study only. It is understood by the Investigator that JJVC will use information developed in this clinical study in connection to the development of the investigational product and therefore may disclose it

as required to other clinical investigators and to regulatory agencies. To allow the use of the information derived from this clinical study, the Investigator must understand that they have an obligation to provide complete test results and all data developed during this study to the Sponsor.

16.3. Data Quality Assurance

Steps will be taken to ensure the accuracy and reliability of data, include the selection of qualified investigators and appropriate clinical sites and review of protocol procedures with the Principal Investigator. The Principal Investigator, in turn, must ensure that all Sub-Investigators and clinical site personnel are familiar with the protocol and all study-specific procedures and have appropriate knowledge of the study article.

Training on CRF completion will be provided to clinical site personnel before the start of the study. The Sponsor will review CRFs for accuracy and completeness remotely during the conduct of the study, during monitoring visits, and after transmission to data management. Any data discrepancies will be resolved with the Investigator or designee, as appropriate.

Quality Assurance representatives from JJVC may visit clinical sites to review data produced during the study and to assess compliance with applicable regulations pertaining to the conduct of clinical trials. The clinical sites will provide direct access to study-related source data/documents and reports for the purposes of monitoring and auditing by JJVC and for inspection by local and regulatory authorities.

17. MONITORING

The study monitors will maintain close contact with the Principal Investigator and the Investigator's designated clinical site personnel. The monitor's responsibilities will include:

- Ensuring that the investigation is being conducted according to the protocol, any subsequent amendments, and regulatory requirements are maintained
- Ensuring the rights and wellbeing of subjects are protected
- Ensuring adequate resources, including facilities, laboratories, equipment, and qualified clinical site personnel
- Ensuring that protocol deviations are documented with corrective action plans, as applicable
- Ensuring that the clinical site has sufficient test article and supplies
- Clarifying questions regarding the study
- Resolving study issues or problems that may arise
- Reviewing of study records and source documentation verification in accordance with the monitoring plan

18. ETHICAL AND REGULATORY ASPECTS

18.1. Study-Specific Design Considerations

Potential subjects will be fully informed of the risks and requirements of the study and, during the study, subjects will be given any new information that may affect their decision to continue participation. Subjects will be told that their consent to participate in the study is voluntary and may be withdrawn at any time with no reason given and without penalty or loss of benefits to which they would otherwise be entitled. Only subjects who are fully able to understand the risks, benefits, and potential adverse events of the study, and provide their consent voluntarily will be enrolled.

18.2. Investigator Responsibility

The Principal Investigator is responsible for ensuring that the clinical study is performed in accordance with the signed agreement, the investigational plan, Section 4 of the ICH E6 guidelines on Good Clinical Practice (GCP),² and applicable regulatory requirements. GCP is an international ethical and scientific quality standard for designing, conducting, recording, and reporting studies that involve the participation of human subjects. Compliance with this standard provides public assurance that the rights, safety, and well-being of study subjects are protected, consistent with the principles of the Declaration of Helsinki 64th WMA General Assembly 2013³ and that the clinical study data are credible. The Investigator must maintain clinical study files in accordance with Section 8 of the ICH E6 guidelines on Good Clinical Practice (GCP),² and applicable regulatory requirements.

18.3. Independent Ethics Committee or Institutional Review Board (IEC/IRB)

Before the start of the study, the Investigator (or Sponsor when applicable) will provide the IEC/IRB with current and complete copies of the following documents (where applicable):

- Final protocol and, if applicable, amendments
- Sponsor-approved informed consent form (ICF) (and any other written materials to be provided to the subjects)
- Investigator's Brochure (or equivalent information) and amendments
- Sponsor-approved subject recruitment materials
- Information on compensation for study-related injuries or payment to subjects for participation in the study
- Investigator's curriculum vitae, clinical licenses, or equivalent information (unless not required, as documented by IEC/IRB)
- Information regarding funding, name of the Sponsor, institutional affiliations, other potential conflicts of interest, and incentives for subjects
- Any other documents that the IEC/IRB requests to fulfill its obligation

This study will be undertaken only after IEC/IRB has given full approval of the final protocol, amendments (if any), the ICF, applicable recruiting materials, and subject compensation programs, and the Sponsor has received a copy of this approval. This approval letter must be dated and must clearly identify the documents being approved.

During the study, the Investigator (or Sponsor when applicable) will send the following documents to the IEC/IRB for their review and approval, where appropriate:

- Protocol amendments
- Revision(s) to ICF and any other written materials to be provided to subjects
- If applicable, new or revised subject recruitment materials approved by the Sponsor
- Revisions to compensation for study-related injuries or payment to subjects for participation in the study
- Investigator's Brochure amendments or new edition(s)
- Summaries of the status of the study (at least annually or at intervals stipulated in guidelines of the IEC/IRB)
- Reports of adverse events that are serious, unanticipated, and associated with the test articles, according to the IRB's requirements
- New information that may adversely affect the safety of the subjects or the conduct of the study
- Major protocol deviations as required by the IEC/IRB
- Report of deaths of subjects under the Investigator's care
- Notification if a new Investigator is responsible for the study at the clinical site
- Any other requirements of the IEC/IRB

For protocol amendments that increase subject risk, the amendment and applicable ICF revisions must be submitted promptly to the IEC/IRB for review and approval before implementation of the change(s).

At least once a year, the IEC/IRB will review and reapprove this clinical study. This request should be documented in writing.

At the end of the study, the Investigator (or Sponsor where required) will notify the IEC/IRB about the study completion. Documentation of this notification must be retained at the clinical site and a copy provided to the contract research organization (CRO) or Sponsor as applicable.

